8.2. Efficacy Variables

Primary Efficacy Parameter:	Time from first dose until Symptom Response
Secondary Efficacy Parameters:	
i. Time from first dose until subjects are able to perform 100% of normal activities (i.e., a score of 10 on the scale of 0-10)ii. Proportions of subjects experiencing one or more complications of colds due to EV/RV infection including pneumonia, otitis media, bronchitis, sinusitis, exacerbations of asthma or COPD, worsening of pre-existing health conditions, secondary infections requiring systemic antibiotic use, hospitalization due to cold or complications of the cold, and death due to cold or complications of the cold
Exploratory Efficacy Parameters:	
i. Time to Individual Symptom Responseii. Time to FLU-PRO Domain Responseiv. Time to Return to Usual Healthv. Change in virus titer (quantitative PCR) from baseline to Day 2, from baseline to Day 3, and from baseline to Day 7vi. Proportions of subjects with virus detected in nasopharyngeal swabs collected at each of Days 2, 3 and 7 by culture and by RT-PCRvii. Time to Symptom Response for all subjects treated (ITT population)viii. Time to Symptom Response for subjects infected with individual non-EV/RV viruses

8.3. Response Definitions

Symptom Response:	To be defined based upon a blinded review of symptom scores (pooled for all EV/RV-infected subjects without regard to treatment group assignment) that correlate to the time at which subjects report that they return to usual health (a daily global assessment question). Methodology for the correlation will be defined in the Statistical Analysis Plan. Symptom scores must be maintained at the defined level for at least 2 daily diary periods without any symptom relief medication during those 2 daily diary periods.
Time of Symptom Response:	The start of the first daily diary period in which Symptom Response is achieved and is maintained for at least 2 daily

Time to Symptom Response:	diary periods without any symptom relief medication during those 2 daily diary periods.
Ability to Perform All Normal Activities:	Time (hours) from first dose to the Time of Symptom Response.
Time of Ability to Perform All Normal Activities:	Subject reports a score of 10 on the 0-10 scale for ability to perform normal activities, which is maintained for at least 2 daily diary periods without symptom relief medication during those 2 daily diary periods
Time to Ability to Perform All Normal Activities:	The start of the first daily diary period in which the subject reports a score of 10 on the 0-10 scale for ability to perform normal activities, which is maintained for at least 2 daily diary periods without symptom relief medication during those 2 daily diary periods
Individual Symptom Response:	Time (hours) from first dose to the Time of Ability to Perform All Normal Activities
Time of Individual Symptom Response:	For each individual symptom (n=32), a score of \leq the maximum response value specified in the Symptom Response definition maintained for at least 2 daily diary periods without symptom relief medication during those 2 daily diary periods
Time to Individual Symptom Response:	The start of the first daily diary period in which the Individual Symptom Response is achieved and is maintained for at least 2 daily diary periods without symptom relief medication during those 2 daily diary periods
FLU-PRO Domain Response:	Time (hours) from first dose to Time of Individual Symptom Response
Time of FLU-PRO Domain Response:	For each individual domain (n=6), each item scored \leq the maximum response value specified in the Symptom Response definition maintained for at least 2 daily diary periods without symptom relief medication during those 2 daily diary periods
	For each domain, the start of the first daily diary period in which the FLU-PRO Domain Response is achieved and is maintained for at least 2 daily diary periods without

	symptom relief medication during those 2 daily diary periods
Time to FLU-PRO Domain Response:	Time (hours) from first dose to FLU-PRO Domain Response for each domain
Return to Usual Health:	“Yes” response to the daily FLU-PRO global assessment question, “Have you returned to your usual health today?” maintained for at least 2 daily diary periods without symptom relief medication during those 2 daily diary periods
Time of Return to Usual Health:	The start of the first daily diary period in which Usual Health is achieved and is maintained for at least 2 daily diary periods without symptom relief medication during those 2 daily diary periods
Time to Return to Usual Health:	Time (hours) from first dose to Time of Return to Usual Health
Complication of Colds:	Complications of colds due to EV/RV infection include pneumonia, otitis media, bronchitis, sinusitis, exacerbations of asthma or COPD, worsening of pre-existing health conditions, secondary infections requiring systemic antibiotic use, hospitalization due to cold or complications of the cold, and death due to cold or complications of the cold. Exacerbations of asthma, exacerbations of COPD, bacterial pneumonia, acute bacterial otitis media and acute bacterial sinusitis will be reported as complications of colds due to EV/RV infection only if each of the following criteria are satisfied:
Exacerbation of asthma:	
1. Episode requires treatment with systemic corticosteroids, and	
2. Episode is considered by the Investigator to be related to viral respiratory infection	
Exacerbation of COPD:	
1. Episode requires a change in regular medication (e.g., addition of antibiotics and/or oral corticosteroids), and	
2. Episode is considered by the Investigator to be related to viral respiratory infection	
Bacterial pneumonia:	

1. At least two of the following symptoms: difficulty breathing, cough, production of purulent sputum, chest pain, and
2. At least two of the following vital sign abnormalities: fever, hypotension, tachycardia, tachypnea, and
3. At least one of the following findings: hypoxemia, clinical evidence of pulmonary consolidation, elevated white blood cell count or leukopenia, and
4. Chest radiograph findings of new infiltrates in a lobar or multilobar distribution, and
5. Microbiologic criteria: appropriate sputum specimen with fewer than 10 squamous epithelial cells and more than 25 polymorphonuclear cells per low power field

Acute bacterial otitis media:

1. Symptoms of ear pain or earache, ear fullness or decreased hearing, and
2. One or more of the following otoscopic findings performed by a clinician experienced in otoscopy:
 - Bulging or fullness of the tympanic membrane (convexity of the plane of the eardrum), with loss of anatomic landmarks on visualization,
 - Opacification of the tympanic membrane regardless of color,
 - Erythema of the tympanic membrane, or
 - Abnormal tympanic membrane mobility on biphasic pneumatic otoscopy; a tympanic membrane in the neutral position or retracted is not sufficient evidence of acute bacterial otitis media because these findings are not specific enough to distinguish the disease from otitis media with effusion

Bacterial sinusitis:

1. At least two of the following symptoms:
 - Maxillary tooth pain (unilateral findings can be more specific)
 - Facial pain (unilateral findings can be more specific)
 - Frontal headache

- Purulent nasal discharge (unilateral findings can be more specific)
- New onset fetor oris (bad breath)
- Morning cough
- Nasal obstruction, and

2. At least one of the following signs:
 - Purulent secretions from sinus ostia on examination
 - Abnormal sinus transillumination
 - Pain on palpation over sinuses
 - Facial swelling, and
3. Radiographic findings consistent with acute sinusitis

8.4. Statistical Methodology

The statistical methodology is described briefly below and will be described in detail in the Statistical Analysis Plan.

8.4.1. Efficacy Analyses

Efficacy analyses will be based on a population consisting of all subjects that received at least one dose of study drug and had laboratory-documented EV/RV infection (infected intent-to-treat or ITTI population). Laboratory-documented EV/RV infection is defined by identification of EV/RV in nasopharyngeal secretions by RT-PCR at baseline, Day 2 or Day 3. For time to event analyses a test of significance (as described in the following) will be performed with descriptive statistics provided including the use of Kaplan-Meier figures.

There will be one primary efficacy analysis:

- Time to Symptom Response for the NTZ treatment group will be compared to that of the placebo treatment group using a stratified Gehan-Wilcoxon test ($\alpha = 0.05$) where stratification will follow that used for randomization. Subjects without a Symptom Response being recorded will be treated as censored as of their last diary without a documented Symptom Response.

If the primary analysis is significant at the 0.05 level, a key secondary efficacy analysis will be formally evaluated at the 0.05 level as follows:

- Time to Ability to Perform All Normal Activities for the two treatment groups will be compared using a stratified Gehan-Wilcoxon test ($\alpha = 0.05$) where stratification will follow that used for randomization. Subjects without an Ability to Perform All Normal Activities response being recorded will be treated as censored as of their last diary without a documented Ability to Perform All Normal Activities response.

If both the primary analysis and the key secondary efficacy analysis are significant at the 0.05 level, another secondary efficacy analysis will be formally evaluated at the 0.05 level as follows:

- Proportions of subjects experiencing one or more complications of colds due to EV/RV infection will be compared between the treatment groups using a Cochran-Mantel-Haenszel test stratified by the randomization strata ($\alpha = 0.05$).

Exploratory analyses will be performed as follows:

- For each of the 32 individual FLU-PRO symptoms, Time to Individual Symptom Response for the NTZ and placebo treatment groups will be compared using the Gehan-Wilcoxon test.
- For each of the 6 FLU-PRO domains, Time to FLU-PRO Domain Response for the NTZ and placebo treatment groups will be compared using the Gehan-Wilcoxon test.
- Time to Return to Usual Health for the NTZ and placebo treatment groups will be compared using the Gehan-Wilcoxon test.
- Changes in viral titers from baseline to Day 2, from baseline to Day 3, and from baseline to Day 7 for the NTZ and placebo treatment groups will be compared using a t-test.
- For subjects with laboratory-confirmed EV/RV, the proportions of subjects with EV/RV detected by culture in nasopharyngeal swabs collected at each of Days 2, 3 and 7 will be compared for the two treatment groups using a Fisher's exact test.
- For the ITT population, Time to Symptom Response for the NTZ and placebo treatment groups will be compared using the Gehan-Wilcoxon test.
- For subsets of subjects infected with individual non-EV/RV viruses (e.g., coronavirus), Time to Symptom Response for the NTZ and placebo treatment groups will be compared using the Gehan-Wilcoxon test.

Sensitivity analyses for the primary endpoint will include:

- Repeat the primary efficacy analysis, assigning a Time to Symptom Response of 21 days for subjects that discontinue prior to Day 21 without achieving Symptom Response.
- Repeat the primary efficacy analysis for a "per protocol" subset.
- Repeat the primary efficacy analysis excluding NTZ-treated subjects who reported experiencing chromaturia.

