Zealand between March 2013 and April 2015. 1,941 subjects 13 to 65 years of age were enrolled based upon symptoms and the presence of influenza in the community. Subjects were enrolled within 48 hours of symptom onset and randomized to receive NTZ 600 mg, OST 75 mg, NTZ 600 mg plus OST 75 mg or placebo twice daily for five days. Nasopharyngeal swabs were collected at baseline for identification of 19 different viral respiratory infections by RT-PCR. Subjects maintained diaries to record time of medication intake, oral temperature, the severity of each of 7 symptoms (cough, nasal obstruction, sore throat, fatigue, headache, myalgia or feverishness graded as absent, mild, moderate or severe), ability to perform normal activities (scale of 0-10), time lost from work or school, concomitant medications and adverse events. Diary data was recorded twice daily through study Day 14 or, if longer, until the subject no longer had any moderate or severe influenza symptoms. Subjects returned to the clinic for follow-up on Day 7, Day 14 and Day 28. Blood and urine samples were collected at baseline and Day 7 for laboratory safety tests, and blood samples were collected at baseline and Day 28 for influenza antibody titer. The primary efficacy endpoint was time from first dose to alleviation of symptoms (all 7 symptoms absent or mild and remained so for at least 24 hours). In accordance with the study statistical analysis plan, the primary efficacy analysis was repeated for the subset of subjects with EV/RV infection.

Two hundred twenty-eight (228) subjects enrolled were diagnosed with EV/RV as the sole infection at baseline. A virus species was identified by sequencing for 86% of these subjects. Sixty-four percent (64%) were *Rhinovirus A*, 12% *Rhinovirus B*, 23% *Rhinovirus C*, and 1% were either *Enterovirus A* or *Enterovirus B*. Within each species there was a wide range of serotypes. Analyses of response data for these subjects are presented below as background and serve in part as the basis for hypotheses tested in the present study (RM08-3005).

In subjects with EV/RV identified as the sole cause of respiratory illness at baseline, treatment with NTZ was associated with a reduction of time to alleviation of symptoms compared to treatment with placebo or OST.

Table 4: Study RM08-3002: Median (IQR) time (hrs.) to alleviation of all symptoms for subjects infected with EV/RV as sole identified pathogen

Group	NTZ	OST	NTZ+OST	Placebo

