5.2. Baseline (day 1, same day as screening evaluation)

At baseline, the following procedures will be carried out:

1. Collection of two nasopharyngeal swabs (one from each nostril) using nylon flocked dry swabs (Copan Diagnostics) for RT-PCR and culture.
2. Collection of blood sample for laboratory safety tests.
3. Collection of a urine sample for routine urinalysis (glucose, protein and blood).
4. Review and recording of any concomitant medications.
5. Provision of an electronic diary to subject via his/her own smartphone or a provisioned device, and subject completion of baseline electronic diary under supervision and instruction of study site personnel, including the Practice Diary, FLU-PRO Questionnaire, Activity Diary, and Study Drug Intake and Temperature Diary.
6. Randomization and dispensing of study medication (medication assigned in sequential order).

7. Administration of the first dose of study medication with food (< 1 hour after food intake) under observation of Investigator or a member of Investigator's staff, and entry in Study Drug Intake and Temperature Diary.
8. Instruct subject regarding:
 - a. *Administration of study medication.* Subjects will be instructed to take the study medication (two tablets) twice daily with food (< 1 hour after food intake, preferably a high-fat meal but at a minimum a cereal bar). The subject should take his/her second dose as close as possible to 12 hours after the first dose. Then he/she will take the study medication every 12 hours for the remaining 4 days.
 - b. *Completion of subject diary.* Subjects will be instructed on completion of the electronic diary.
 - c. *Use of birth control.* Female subjects of childbearing potential, if sexually active, will be instructed to continue an acceptable method of birth control for the duration of the study and for 1 month post-treatment. Acceptable methods of birth control include a double barrier method, oral birth control pills, an IUD, or medroxyprogesterone acetate administered intramuscularly.
 - d. *Follow-up visits:* Subjects will be instructed to return to the clinic for follow-up on Day 7 and Day 22.
 - e. *Seeking emergency care or contacting the study physician or nurse:* Subjects must be informed to seek emergency medical care or contact the study physician or nurse if they develop any of the following symptoms listed below during the full 22-day study and follow-up period.

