5.5. Day 2 and 3 Evaluations

A study physician, nurse or other study personnel will visit each subject at home (or at the clinic or another location as agreed with the subject) on each of Days 2 and 3 to (i) collect two nasopharyngeal swabs for detecting and quantifying EV/RV, and (ii) screen for potential complications and adverse events. Subjects will be referred for immediate care as needed based on the screening. All information gained from these visits will be included in the case report forms for each subject. In addition, a blood sample for pharmacokinetics will be collected on Day 3. The Day 2 and Day 3 visits will occur at approximately the same time of day that the patient took his/her first dose of study medication (approximately 24 and 48 hours after the first dose). On Day 3, the blood sample for pharmacokinetics will be collected before the first dose of that day.

Study sites or subjects may opt out of these Day 2 and Day 3 visits due to site staffing, subject availability or other practical considerations or preferences; nevertheless at least 75% of subjects enrolled in the trial are expected to complete the Day 2 and Day 3 visits and related procedures (for viral kinetics and pharmacokinetics).

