5.12. Plan for Virology Testing and Monitoring Resistance

Virology testing of nasopharyngeal swab samples will be conducted as described on the following pages.

Table 10: Virology testing of nasopharyngeal swabs

	Day 1	Day 2	Day 3	Day 7	Day 22
RT-PCR by ePlex RPP for Virus Detection	X	X ¹	X ²	X ³	X ⁴
Sequencing for EV/RV Typing	X ⁵				
Quantitative PCR	X ⁶	X ⁶	X ⁶	X ⁷	
Culture & Susceptibility Testing for Resistance Monitoring	X ⁸			X ⁸	X ⁸
Nucleotide Sequencing	X ⁹			X ⁹	X ⁹

¹ If Day 1 sample is negative for EV/RV by RT-PCR² If Day 2 sample is negative for EV/RV by RT-PCR³ Only if one of Day 1, 2, or 3 samples is positive for EV/RV for RT-PCR⁴ If Day 7 sample is positive for EV/RV by RT-PCR⁵ Only the earliest sample positive for EV/RV by RT-PCR of those collected at Days 1, 2, and 3 will be sequenced for EV/RV type⁶ A sample will only be subjected to quantitative PCR if one of the Day 1, 2, or 3 samples is positive for EV/RV by RT-PCR⁷ The Day 7 sample will be subjected to quantitative PCR only if one of the Day 1, 2, or 3 samples AND the Day 7 sample is positive for EV/RV by RT-PCR⁸ If the Day 1 and Day 7 or Day 1, 7, and 22 samples are positive for EV/RV by RT-PCR each sample will be cultured and tested for susceptibility to tizoxanide. Results observed for the Day 7 and Day 22 samples will be compared to the results observed for the Day 1 sample.⁹ Sample pairs exhibiting resistance to tizoxanide will be subjected to sequencing.

1. Collection of samples:

Two nasopharyngeal swabs will be collected from each subject at Baseline (Day 1) and Days 2, 3, 7 and 22.

2. Testing of biological samples:

a. Each Baseline sample will be subjected to RT-PCR using the ePlex® Respiratory Pathogen Panel (GenMark, Carlsbad, CA) to detect influenza A (non-specific as to subtype); influenza A H1, H1N1 (2009), H3 subtypes; influenza B; respiratory syncytial virus A and B (RSV); parainfluenza 1, 2, 3 and 4; human metapneumovirus (hMPV); adenovirus; human EV/RV; coronavirus NL63, HKU1, 229E and OC43; human bocavirus; *Chlamydophila pneumoniae*; *Legionella pneumophila*; and *Mycoplasma pneumoniae*.

b. If a subject's Baseline sample is negative for EV/RV by RT-PCR, his/her Day 2 and Day 3 samples will be subjected to RT-PCR using the ePlex® Respiratory Pathogen Panel to detect respiratory pathogens.

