c. If the Baseline sample or the Day 2 or Day 3 sample is positive for EV/RV, the earliest positive sample will be sequenced to determine virus type and each of the Baseline, Day 2 and Day 3 samples will be subjected to quantitative PCR testing to quantify viral shedding.

d. All Day 7 samples will be subjected to RT-PCR using the ePlex® Respiratory Pathogen Panel. Day 7 samples positive for EV/RV will also be subjected to

quantitative PCR testing to quantify viral shedding if one of the Day 1, 2, or 3 samples was also positive for EV/RV.

- e. Day 22 samples will be subjected to RT-PCR using the ePlex® Respiratory Pathogen Panel only if the sample collected at the preceding time point (Day 7) had detectable EV/RV.
3. Drug susceptibility testing:
 - a. If any Day 7 or Day 22 sample is positive for EV/RV by RT-PCR and one of the Day 1, 2, or 3 samples was also positive for EV/RV, the virus will be isolated (if possible) and tested for susceptibility to tizoxanide (TCID₅₀).
 - b. The Baseline isolate for subjects with virus cultured at Day 7 or 22 will also be tested for susceptibility to tizoxanide, and the results will be compared to the results observed for the Day 7 or 22 isolate.
4. Nucleotide sequencing:
 - a. All Day 7 or 22 samples with resistance ($IC_{50} \geq 10x IC_{50}$ at Baseline) to tizoxanide will be subjected to sequencing. The corresponding Baseline sample will also be subjected to nucleotide sequencing. Initial genotypic assessments of resistance to tizoxanide will focus on isolates displaying the largest shifts in susceptibility.
 - b. Sequencing data for Day 7 or 22 isolates with resistance to tizoxanide will be compared to sequence data for the Baseline sample to identify mutations that may confer resistance.
5. Storage of samples: All samples collected during the study will be stored for at least 2 years for potential future testing.
6. Clinical Virology Laboratory for diagnostic testing:
[REDACTED]

7. Clinical virology laboratory for sequencing, quantification of viral shedding, and susceptibility testing:
[REDACTED]

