**Table 2: Definition of Analysis Populations**

Table Analysis Population	Definition
Intent to Treat (ITT)	All subjects who receive at least one dose of study medication
Intent to Treat Infected (ITI)	The subset of the ITT population who are positive for EV/RV by RT-PCR at any of the Baseline, Day 2 or Day 3 visits
Per Protocol	The subset of the ITI population with no major protocol deviations that may have an effect on the integrity of the data or the evaluation of effectiveness

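### The primary (ITTI) population admits baseline-negative subjects on RT-PCR taken after dosing, and no analysis of Time to Symptom Response is limited to subjects positive before dosing

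*Protocol*

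**What the plan says.** Protocol 8.4.1 requires at least one dose and documented infection for the efficacy population: "Laboratory-documented EV/RV infection is defined by identification of EV/RV in nasopharyngeal secretions by RT-PCR at baseline, Day 2 or Day 3". SAP Table 2 gives the same rule for ITTI: "The subset of the ITT population who are positive for EV/RV by RT-PCR at any of the Baseline, Day 2 or Day 3 visits".

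The three swabs stand differently in relation to treatment. In Protocol 5.2 the baseline swab is item 1 and the first dose is item 7. Protocol 5.5 places the Day 2 and Day 3 visits about 24 and 48 h after the first dose and makes them optional: "Study sites or subjects may opt out of these Day 2 and Day 3 visits due to site staffing, subject availability". At least 75% of subjects are expected to complete them.

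Protocol 5.12 (item 2b) sets out the retesting: if a subject's "Baseline sample is negative for EV/RV by RT-PCR, his/her Day 2 and Day 3 samples will be subjected to RT-PCR". Quantitative PCR is conditional as well. Table 10, note 6 says: "A sample will only be subjected to quantitative PCR if one of the Day 1, 2, or 3 samples is positive for EV/RV". When that condition is met, item 2c states that "each of the Baseline, Day 2 and Day 3 samples will be subjected to quantitative PCR testing to quantify viral shedding".

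**The concern.** A subject who is EV/RV-negative on Day 1 enters the primary population only through a positive result obtained after randomization and dosing. The protocol reports in vitro activity of NTZ against rhinovirus (1.2.1) and plasma steady state by Day 2 (1.2.2). It aims to start treatment before virus titer peaks (section 3). SAP 11.5.5 compares Day 2/3 positivity between arms as an outcome. A result that treatment may influence therefore helps decide who is analysed.

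If NTZ lowered detection at 24 to 48 h, fewer baseline-negative NTZ subjects would enter ITTI than placebo subjects. If those late entrants also recovered more slowly or faster than others, the arms would differ in prognosis without any effect on symptoms. At stake is whether a primary result, in either direction, could be questioned because part of its population was chosen after dosing.

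A narrower point concerns SAP 11.5.5 itself. Late entrants are in its Day 2/3 denominator because one of those samples was positive. Baseline-positives, who supply most of its results through quantitative PCR, are not affected.

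**Working it through.** **1. The plan's own figures.** 530/(1 − 0.12) = 603 after rounding up, against 600 stated. 700/0.40 = 1,750, as stated. The 90% power at 530 cannot be reproduced, because the day-by-day curves are in a figure that is not available.

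**2. Every planned analysis of Time to Symptom Response.**
- Primary analysis (SAP 11.2.2): ITTI.
- Sensitivity analyses (11.3.1–11.3.3): 21-day assignment, per protocol and chromaturia exclusion, all within ITTI.
- ITT (11.5.6): all dosed subjects, with a separately derived response definition.
- Other viruses or no pathogen (11.5.9): subgroups not defined by EV/RV positivity.
- Time from onset to first dose (11.5.10–11.5.12): subsets of ITTI.
- Plasma concentration (11.6.1): NTZ-treated ITTI only.
- Symptom relief medication (11.6.2): placebo subjects only.

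None is limited to subjects EV/RV-positive before dosing. The only restriction on baseline virus is in the titer-change analysis (11.5.4), a different endpoint. That restriction also uses quantitative PCR.

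**3. Possible number of late entrants.** The late-positive rate is not in the documents, so a range is assumed. Let p be the baseline-positive share of all enrolled, and q the late-positive rate among baseline-negatives who attend. With 1,750 enrolled (875 per arm), 40% in ITTI (350 per arm) and 75% attendance, p + (1 − p) × 0.75 × q = 0.40.

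| q | p | Attending baseline-negatives per arm | Late entrants per arm | Share of ITTI |
|---|---|---|---|---|
| 2% | 0.391 | 400 | 8.0 | 2.3% |
| 5% | 0.377 | 409 | 20.5 | 5.8% |
| 10% | 0.351 | 426 | 42.6 | 12.2% |

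**4. Error rate with no drug effect on symptoms.** This is a simulation of the Gehan test with 300 placebo subjects, a daily grid and censoring at 504 h. Times are lognormal with median 302 h and sigma = ln(643/135)/(2 × 0.6745) = 1.157, from the placebo column of Protocol Table 7. The fitted IQR is 138–659 h, against 135–643 h. There were 200,000 runs per case, with a simulation standard error of about 0.05 point. The late share is that of the placebo arm. Each tail should be 2.5%. Totals differ from the sum of the tails only by rounding.

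| Late share | Detection under NTZ | Recovery time of late-positives | Tail favouring NTZ | Tail against NTZ | Two-sided |
|---|---|---|---|---|---|
| 5% | halved | ×2 | 3.43% | 1.77% | 5.19% |
| 10% | halved | ×2 | 4.72% | 1.12% | 5.84% |
| 5% | halved | ×1.25 | 2.87% | 2.23% | 5.10% |
| 10% | halved | ×1.25 | 3.18% | 1.95% | 5.12% |
| 5% | halved | ×0.5 | 1.68% | 3.46% | 5.14% |
| 10% | halved | ×0.5 | 1.01% | 4.91% | 5.92% |
| 5% | cut 20% | ×2 | 2.86% | 2.11% | 4.98% |
| 10% | cut 20% | ×2 | 3.11% | 1.81% | 4.92% |

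With no change in detection the two-sided error is 4.7–5.1%. With no difference in prognosis it is 4.9–5.1%. A test stratified over 12 equal strata (20,000 runs; detection halved, time doubled) gives 5.1% and 6.0% at the two late shares if late entrants are spread at random. It gives 5.5% and 5.8% if they all fall in one onset category.

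**5. Spurious median difference, placebo minus NTZ, detection halved.** The medians come from the mixture distributions.
- Time doubled: 312.1 − 307.1 = 5.0 h at a 5% share, and about 10 h (322.7 against 312.7) at 10%.
- Time ×1.25: 1.6 and 3.2 h.
- Time halved: −4.7 and −9.1 h.

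The plan assumes a true difference of 48 h.

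**The case against.** The rule is prespecified, identical in both documents and biologically sensible: an early presenter may be swabbed while titer is still rising, and retesting recovers true infections. That stands. This is a design weakness with a missing check, not a contradiction, and it is why ITTI should remain primary.

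The effect is near zero unless strong assumptions combine, and nothing in the documents favours a 10% late share over 2%. That also stands. The simulation uses normal-activities times as a stand-in for symptom times. Under that curve a 48 h shorter median gives only about 37% power at 265 per arm, so it cannot be the curve behind the stated 90%. The decimals are illustrative, and the uncertainty runs both ways: a narrower spread (sigma 0.7) raises the favouring tail to about 6.4% in the worst case.

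Optional attendance matters little under blinding unless it differs by arm, and nothing suggests that it does.

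Other displays help in part. The ITT analyses (SAP 11.5.6–11.5.8) avoid the selection, and the normal-activities endpoint has a fixed definition. The by-arm baseline virus tables (10.1.4) and the virology listing should let late entrants be counted. But the ITT analyses are exploratory, about 60% of their subjects are EV/RV-negative at the planned 40% positive rate, and ITT Symptom Response has its own definition. A difference between ITT and ITTI could reflect dilution, a changed endpoint or selection. Day 2/3 attendance among baseline-negatives is not tabulated.

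Finally, the Symptom Response definition is itself derived from pooled ITTI, late entrants included. Reusing it does not undo that influence, but it holds the endpoint constant, so only membership changes.

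**Conclusion.** The concern holds. Membership of the primary population rests partly on a post-dose result, and no planned analysis of Time to Symptom Response shows whether the primary conclusion depends on those subjects. No bias is demonstrated. It needs both a drug effect on Day 2/3 detection and a different recovery rate in late-positives. Its direction is unknown and its size is probably small, about 5.2% or 5.8% two-sided error in the doubled-recovery scenario at 5% or 10% late shares. Those figures rest on assumed late shares, detection effects, prognosis and a stand-in curve.

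The check should be added because it is cheap and direct, and more credible if specified before unblinding. It is also closer to the RM08-3002 data behind the sample-size assumption (Protocol 1.2.5): "Two hundred twenty-eight (228) subjects enrolled were diagnosed with EV/RV as the sole infection at baseline". The match is not exact, since Day 1 positives here may have co-infections.

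**What to change.** Before unblinding, with ITTI kept as the primary population:

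1. Add a named sensitivity analysis to SAP 11.3. It repeats the primary test, with the Symptom Response definition already selected under 11.2.1, in dosed subjects EV/RV-positive by panel RT-PCR on the pre-dose Day 1 swab. Specify the panel result, not quantitative PCR. A panel-negative Day 1 sample gets quantitative PCR only if a Day 2 or 3 sample is positive, which would bring the post-dose selection back.
2. Tabulate by arm the subjects admitted only at Day 2/3, and Day 2/3 attendance among baseline-negatives.
3. In SAP 11.5.5, restrict the Day 2/3 detection comparison to Day 1 panel-positive subjects, using quantitative PCR. State the population for each day, since the Day 7 comparison would otherwise rest on a different one.

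The cost is SAP wording, one analysis and one table. The Day 1 swab is already taken and panel-tested in every subject, and the primary test and its power are unchanged.

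The added analysis has slightly fewer subjects. Taking 90% at 530 as given, power = Φ(3.2415 × √(n/530) − 1.96):
- 600 in ITTI (530 complete): n = 503.5 gives 88.5% at a 5% late share, and n = 477 gives 86.8% at 10%.
- 700 in ITTI (700 × 0.88 = 616 complete): n = 585.2 gives 92.6%, and n = 554.4 gives 91.2%.

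It also leaves out true infections missed on an early swab, so a somewhat weaker result there is not by itself evidence of bias.
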